5 ADVERSE EVENTS OF INTEREST, SERIOUS ADVERSE EVENTS, CASE AND EXPOSURE DEFINITIONS

Serious adverse events and AEs of interest are the focus of this registry; Investigators are not expected to enter nonserious AEs in the eCRF except for AEs of interest regardless of seriousness.

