5.2 Adverse Events of Interest

- Autoimmune disorders, such as:
 - systemic lupus erythematosus
 - rheumatoid arthritis
- Demyelinating disorders, such as:
 - multiple sclerosis
 - Guillain-Barre syndrome
 - chronic inflammatory demyelinating polyneuropathy
- Serious infections including opportunistic infections, such as:
 - tuberculosis
 - pneumonia
- Lymphoma and other malignancies, such as:

- hepatosplenic T-cell lymphoma
- non-Hodgkin's lymphoma
- solid malignancies
- Acute hypersensitivity reactions occurring within 2 hours of drug administration, such as:
 - urticaria, rash, pruritus, flushing, swollen lips/tongue/pharynx, wheezing, dyspnea, hypotonia, cramping, abdominal pain, and vomiting
- Other events:
 - congestive heart failure
 - aplastic anemia, pancytopenia, thrombocytopenia, neutropenia and leucopenia
 - serious bleeding events
 - serious skin reactions (eg, Stevens Johnson Syndrome, toxic epidermal necrosis, and erythema multiforme)

When available, narrow scope SMQs (Standardized MedDRA Queries) from the Medical Dictionary for Regulatory Activities (MedDRA®) version 17.0 will be used to define the AEs of interest (Section 5.2). Adverse events of interest that are the clinical endpoints for the SECURE registry will be confirmed by review of the results of diagnostic tests and diagnostic criteria used by the Investigator which are further explained within each section below.

Table 5–1: Standardized MedDRA Queries for select adverse events of interest

Event	SMQ Title	SMQ Code	SMQ Scope
Malignancy	Malignant tumours	20000194	Narrow PTs
Congestive Heart Failure	Cardiac failure	20000004	Narrow PTs
Serious skin reactions	Severe cutaneous adverse reactions	20000020	Selected Narrow PTs
Hypersensitivity reactions	Anaphylactic reaction	20000021	Narrow/Broad PTs
Serious bleeding events	Haemorrhage	20000038	Narrow PTs
Aplastic anemia	Haematopoietic cytopenias affecting more than one type of blood cell	20000028	Narrow PTs
Aplastic anemia	Haematopoietic erythropenia	20000029	Narrow PTs

Table 5–1: Standardized MedDRA Queries for select adverse events of interest

Event	SMQ Title	SMQ Code	SMQ Scope
Aplastic anemia	Haematopoietic leukopenia	20000030	Narrow PTs
Aplastic anemia	Haematopoietic thrombocytopenia	20000031	Narrow PTs

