5.4 Adverse Event Reporting to the Registry

Serious adverse events and AEs of interest are the focus of this registry; Investigators are expected to enter all SAEs and AEs of interest in the eCRF.

All SAEs and all AEs of interest will be entered in the EDC system within 24 hours of site notification and will be automatically forwarded to PRA, International for assessment and further processing as per regulatory requirements and UCB procedures (see [Figure 5-1](#), Event Reporting Process for flow of activity).

Any major changes in health status reported by the patient during the every 3 month patient follow-up will be sent to the Investigator for medical confirmation. Once medical confirmation is obtained, the Investigator will report the event through the EDC system.

To ensure the capture of any events that might occur between patient or Investigator data entry intervals, each patient will be provided a safety reporting process patient card that they

can present to an Investigator if they have an event. The card will contain instructions for the Investigator on how to report event information.

Information and instructions informing patients about the Follow-Up Period and how to report AEs is included in the Informed Consent Form. More detailed instructions to sites regarding reporting of SAEs and AEs of interest are provided in the UCB safety Guidance booklet.

[figure not shown]

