- Any changes in medication
- Any administrative changes such as change in contact information

Change #9 Section 9 Adverse events of interest, serious adverse events, case and exposure definitions

New text added –

Although serious adverse events and nonserious adverse events of interest are the focus of this registry, Investigators are expected to enter all AEs in the eCRF.

Change #10 Section 9.2 Adverse events of interest

New text (final bullet) –

- Other events:
 - Congestive heart failure
 - Aplastic anemia, pancytopenia, thrombocytopenia, neutropenia and leucopenia
 - Serious bleeding events
 - Serious skin reactions (eg, Stevens Johnson Syndrome, toxic epidermal necrosis, and erythema multiforme)

Change #11 Section 9.3 Anticipated serious adverse events (new section)

New text -

The following list of Anticipated SAEs has been identified as these events are anticipated to occur in the population studied in this protocol at some frequency that is independent of drug exposure. This original list will remain in effect for the duration of the protocol.

This list does not change the Investigator's obligation to report all serious AEs (including Anticipated SAEs) as detailed in Section 9.7.

Crohn's disease
perianal abscess
abdominal pain

Change #12 Section 9.5 Exposure definition

Old text -

Cimzia Exposure:

Cimzia exposure will be calculated by two methods. The first method will assume exposure from day one of the first dose of Cimzia medication regardless of medication discontinuation through the date of the last follow-up evaluation. The second method will be a series of

sensitivity analyses and stratifications to evaluate the different clinically driven definitions of exposure to drug. Specifics to these definitions will be outlined in the SAP.

Control Exposure:

Non-Cimzia® medication exposure will be calculated by two methods. The first method will assume exposure from day one of the first dose of the non-Cimzia® medication regardless of medication discontinuation through the date of the last follow-up evaluation. The second method will be a series of sensitivity analyses and stratifications to evaluate the different clinically driven definitions of exposure to drug. Specifics to these definitions will be outlined in the SAP.

Has been changed to –

Cimzia Exposure:

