3.6 Treatment assignment and treatment groups

Given that patients will be followed for 8 years, it is anticipated that patients will switch CD medications while enrolled in the registry. Therefore, a patient's treatment at registry enrollment will most likely not reflect their exposure throughout the study. Three comparisons may be used to reflect these treatment changes over time and provide context for events reported to the registry. See Section 8.1.4 for details.

Treatment start is the recording period (ie, the informed consent date). Only study emergent adverse events will be reported. Study emergent begins at the informed consent through the end of the study.

Treatment by enrollment cohort will consist of two groups:

- Cimzia
- Comparator
 - where comparator includes:
 - Corticosteroids
 - Immunosuppressants
 - Other biologics (e.g. anti-TNFs) other than Cimzia

Enrollment cohort is recorded and will be assumed regardless of the presence of prior or imputed CD medication referring to the other treatment group. These are the default treatment groups.

Some summaries will be repeated by actual treatment at Baseline to examine differences between treatment by enrollment cohort. Actual treatment at Baseline will be summarized in three groups:

- Cimzia at BL
- No Cimzia at BL
- Gap (absence of Cimzia and comparator)

Actual treatment will be used for adverse event tables unless specified otherwise. If a patient received Cimzia up to 70 days prior to baseline (half-life of CZP), the patient is a member of the treatment group "Cimzia at BL". For the calculation of the Hazard Ratio, the group 'Cimzia at BL' is compared against the combined group "No Cimzia at BL" and "Gap".

For malignancies, person-time and events will be categorized into 2 groups:

- Cimzia
- Comparator

where a patient is systematically attributed to Cimzia from their first dose of Cimzia until the end of the study, even after ending or switching from Cimzia.

For acute events, person-time and events will be categorized into 5 groups:

- Cimzia
- Comparator
- Overlap (Cimzia and comparator)
- Gap (absence of Cimzia and comparator)
- Any Cimzia (Cimzia and Overlap)

Example treatment allocations for malignancies and acute events are in Section 11.1, appendix 1.

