- Serious skin reactions (eg, Stevens-Johnson Syndrome, toxic epidermal necrosis, and erythema multiforme). These will be manually identified by the study physician from Serious TEAE table.

Although not officially AEs of interest, the following events will also be summarized as described in the AEs of Interest – Cimzia Program 2018-01-05 guidance document.

- Hepatic events. These will consist of a subset of all TEAEs, identified using the following 5 SMQs: Cholestasis and jaundice of hepatic origin; Hepatic failure, fibrosis, and cirrhosis and other liver damage-related conditions; Hepatitis, noninfectious; Liver-related investigations, signs and symptoms; and Liver-related coagulation and bleeding disturbances.
- Hypersensitivity reactions and anaphylactic reactions. Hypersensitivity reactions will be summarized as any TEAEs occurring on the same day or the day after injection was received, which code to the following preferred terms: Administration site hypersensitivity, Documented hypersensitivity to administered product, Drug hypersensitivity, Hypersensitivity, Hypersensitivity vasculitis, Infusion site hypersensitivity, Injection site hypersensitivity, Medical device site, hypersensitivity, Type II hypersensitivity or Type IV hypersensitivity reaction. Anaphylactic reactions will be defined using an algorithmic approach as described in the “AEs of Interest – Cimzia Program 2018-01-05” guidance document.
- Specific to study and not from the “AEs of Interest – Cimzia Program 2018-01-05” guidance document, we will also look at Malignant Lymphomas using the Narrow PTs from the “Malignant Lymphomas” SMQ, and into Autoimmune disorders and Lupus/Lupus-Like syndromes.
- Specific to study and not from the “AEs of Interest – Cimzia Program 2018-01-05” guidance document, we will also look at cases of non-melanoma Skin Cancer. These will be manually identified by the study physician from the TEAE table.

Table 8.1: Overview of malignancy events and acute events in this study

Overview of Events	
Event	Event Type (Malignancies are in addition analyzed following acute rules)
Malignant or unspecified tumor	Malignancy
Malignant tumor	Malignancy
Non melanoma skin cancer	Malignancy
Malignant Lymphoma	Malignancy
Serious infection	Acute
Opportunistic infection	Acute
Serious cardiac event	Acute
Congestive heart failure	Acute
Demyelinating-like disorder	Acute
Aplastic Anemia	Acute
Serious bleeding	Acute
Lupus and Lupus-like illness	Acute

Serious skin reaction	Acute

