Hepatic event	Acute
Hyper/Anaphylactic reaction	Acute
Autoimmune Disorder	Acute

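### The SAP builds its hepatic-event outcome from all TEAEs, although the protocol requires sites to enter only the serious ones

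*SAP*

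**What the plan says.** **SAP.** Section 8.2.3 introduces hepatic events with the words "Although not officially AEs of interest, the following events will also be summarized" and then defines them: "Hepatic events. These will consist of a subset of all TEAEs, identified using the following 5 SMQs". One of the five SMQs covers liver-related investigations, signs and symptoms. Table 8.1 has a row "Hepatic event" with event type acute. Section 3.6 then applies: "For acute events, person-time and events will be categorized into 5 groups". Section 8.1 obtains rates by dividing reported events by patient-years at risk and compares Cimzia with other treatments. Section 8.2.2 takes AEs from investigator reports and a drug safety database excerpt, and excludes events known only from the patient survey.

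**Protocol.** Section 5 states: "Investigators are not expected to enter nonserious AEs in the eCRF except for AEs of interest regardless of seriousness". Section 5.4 puts it positively: "Investigators are expected to enter all SAEs and AEs of interest in the eCRF". The list in section 5.2 includes, for example, "aplastic anemia, pancytopenia, thrombocytopenia, neutropenia and leucopenia". It has no hepatic entry, and neither Table 5–1 nor the endpoint list in section 6.1.1 adds one.

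**Collection history.** The amendment log is superseded text and is used here only to show what sites were asked for at different times. Amendment 2 (section 14.2, Change #9) introduced "Investigators are expected to enter all AEs in the eCRF". Amendment 3 (section 14.3, Change #17) withdrew it.

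**The concern.** The SAP counts a class of event that the protocol does not ask sites to record. A site that follows the current protocol enters a serious hepatitis. It need not enter a nonserious rise in liver enzymes, unless that event also falls under a listed AE of interest. The nonserious part of the numerator therefore depends on which sites volunteered events and on the entry rule in force at the time, while person-time is counted in full.

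The resulting figure is neither a rate of all hepatic events nor a rate of serious ones. A reader who takes it as the former would think hepatic events rarer than they were. If volunteering also differed between Cimzia and comparator exposure, the comparison would carry that difference as well.

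**Working it through.** The plan gives no hepatic rate, so there is no figure to reproduce. The check sets the texts side by side and then illustrates the size under stated assumptions.

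**1. Numerator against collection**

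| Part of the hepatic numerator | Counted under SAP 8.2.3 | Entry required by Protocol 5 and 5.4 |
|---|---|---|
| Serious events | yes | yes |
| Nonserious events | yes | no (not an AE of interest) |

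Patient-survey events cannot fill the second row, because SAP 8.2.2 excludes them.

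**2. The filter used elsewhere in the same section.** SAP 8.2.3 limits cytopenias, bleeding and serious cardiovascular events to serious TEAEs. Cytopenias are a protocol AE of interest, so sites had to enter them whether serious or not. The narrower numerator is thus applied where nonserious collection was required, and the wider one where it was not.

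**3. Entry rule over calendar time.** Inputs are the amendment dates on the title-page table in section 14.3 and the study end of 28 August 2020 in SAP 2.3.

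- 06-Jan-2009 to 24-Jun-2009, 0.46 years: other AEs at the investigator's judgment.
- 24-Jun-2009 to 05-Dec-2011, 2.45 years: SAEs and nonserious AEs of interest.
- 05-Dec-2011 to 04-Dec-2013, 2.00 years: all AEs.
- 04-Dec-2013 to 28-Aug-2020, 6.73 years: nonserious AEs not expected, with the exception for AEs of interest in the current text.

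The total is 0.46 + 2.45 + 2.00 + 6.73 = 11.64 years. All-AE entry covers 2.00/11.64 = 17% of calendar time, and the period after Amendment 3 covers 6.73/11.64 = 58%. These are shares of calendar time by amendment date. They are not shares of person-time, and they ignore when each site adopted an amendment.

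**4. Size of the understatement.** Let f be the nonserious share of true hepatic TEAEs and c the probability that a nonserious event is entered. Take serious events as fully captured, which is a simplification. Then

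observed rate / true rate = (1 − f) + f·c.

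The documents give neither f nor c. The assumed ranges are f = 0.3 to 0.9 and c = 0.10 to 0.50.

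- Mildest: f = 0.3, c = 0.50 gives 0.70 + 0.15 = 0.85.
- Middle: f = 0.5, c = 0.25 gives 0.50 + 0.125 = 0.625.
- Most severe: f = 0.9, c = 0.10 gives 0.10 + 0.09 = 0.19.

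**5. Effect on the rate ratio when the true ratio is 1.** Let c1 apply to Cimzia and c0 to comparator, with the same f in both:

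observed ratio = [(1 − f) + f·c1] / [(1 − f) + f·c0].

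- Equal capture, c1 = c0: the ratio is 1.0 for every f.
- f = 0.3, capture 0.30 against 0.20: 0.79/0.76 = 1.04.
- f = 0.9, capture 0.50 against 0.10: 0.55/0.19 = 2.89.
- With the capture values exchanged, these become 0.76/0.79 = 0.96 and 0.19/0.55 = 0.35.

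For the nonserious part alone the ratio is simply c1/c0. Assumed values of 0.40 and 0.25 give 1.6, and the reverse gives 0.63. All the figures in steps 4 and 5 illustrate the mechanism and are not estimates.

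**The case against.** The strongest reply is that little rests on this outcome. Hepatic events are not a protocol endpoint, the SAP states that all analyses are descriptive without formal hypothesis testing, and it says only that hepatic events will be summarized as described in a guidance document that is not available here. SAP 8.1.3 and 8.1.4 frame time-to-event and rate analyses around AEs of interest, which the SAP says hepatic events officially are not. SAP 8.2.2 and 8.2.4 already provide SAE tables and a listing of all eCRF AEs. Enrollment was to be balanced over time, and calendar year of enrollment is a covariate.

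Much of this stands. A hepatic rate is a fair inference from Table 8.1 read with sections 3.6 and 8.1, but no sentence states it. The existing SAE tables show serious hepatic terms by SOC, HLT and PT, though not as an SMQ group. Balanced enrollment and the covariate give partial protection to a comparison. They do not restore missing events to an absolute rate, nor fully handle an entry rule that changes during a patient's follow-up. A descriptive rate with incomplete capture is still too low.

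Several stronger readings are tempting, and the documents do not support them:

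- **That sites were told not to enter nonserious hepatic events.** Protocol section 5 says such entry is not expected. It is a general rule, not a ban, and does not name hepatic events.
- **That the safety database adds Cimzia cases only and so creates unequal capture.** Protocol 5.6 says that events collected from the registry within 70 days of a Cimzia dose go into the sponsor's database. The registry feeds the database, so this does not show extra Cimzia events that sites never entered. SAP 8.2.2 says the two sources were reconciled.
- **That a hepatic hazard ratio is planned.** None is stated explicitly.
- **That serious events are completely collected.** Their entry is required, but no visits are mandatory and completeness is not shown.

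**Conclusion.** The mismatch between numerator and required collection is in the text and needs no assumption. It affects only the nonserious part of the hepatic outcome. An all-TEAE hepatic rate understates the true all-event rate to the extent that sites did not volunteer nonserious events. Under the assumed ranges the observed rate is 19% to 85% of the true one. Bias in the Cimzia/comparator ratio is conditional: it requires optional entry to differ by treatment, which the documents do not show, and with equal capture the ratio is unaffected. The unequal-capture results (1.04 to 2.89, or 0.96 to 0.35 in the other direction, and 1.6 or 0.63 for the nonserious part alone) should not be read as expected bias. The outcome is an addition to the protocol's list, so the stakes are modest. The change is worth making because it is specific, nearly free and matches what the same SAP section already does.

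**What to change.** In SAP 8.2.3, base any hepatic incidence rate, event rate or treatment comparison on the subset of serious TEAEs in the 5 SMQs, as the section does for cytopenias and bleeding. Show nonserious hepatic events in a separate row or listing, with a footnote that the protocol did not require their entry and that they support no comparative rate. If no hepatic rate is intended at all, say so beside Table 8.1.

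This needs a changed definition and a footnote, and no new data. The price is fewer hepatic events, wider intervals, and a comparative rate that departs from the program-wide definition; the separate display of nonserious events keeps those events visible.

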5.2.5 Hypersensitivity Reaction

Primary endpoints for hypersensitivity reaction are events meeting the criteria of an anaphylactic reaction and acute hypersensitivity reaction occurring within 2 hours of drug administration. As described in the case definition below, anaphylactic events include all terms listed in Category A, which consists of the narrow terms Type I hypersensitivity, anaphylactic shock and anaphylactoid reaction. In addition, combinations of the AE terms listed in Categories B, C and D will also be defined as anaphylactic events.

Category A: anaphylactic reaction, Type I hypersensitivity, anaphylactic shock, anaphylactoid reaction

Category B: dyspnoea, chest discomfort, cough, swollen tongue, oedema mouth, throat tightness, wheezing, laryngeal oedema, respiratory distress, sensation of foreign body, asthma, sneezing

Category C: swelling face, urticaria, pruritus, rash, eye swelling, pruritus generalized, rash, generalized, flushing, erythema, swelling, eye pruritus, lip swelling, rash pruritic, rash, erythematous, eyelid oedema, ocular hyperaemia, injection site urticaria, angioedema

Category D: hypotension, blood pressure decreased

To meet the definition of an anaphylactic event, a case has to meet one of the following criteria:

1. A narrow term or a term from Category A;
2. A term from Category B (Upper Airway/Respiratory) AND a term from Category C (Angioedema/Urticaria/Pruritus/Flush);
3. A term from Category D (Cardiovascular/Hypotension) AND either a term from Category B (Upper Airway/Respiratory) or a term from Category C (Angioedema/Urticaria/Pruritus/Flush)

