3.2.1.3 Determination of Event Rate Numerator

The number of events will be determined for Cimzia and for all other CD treatments considered comparator treatments based on the date of the last dose received before event onset and treatment class-specific half-life exposure of the medication. The exposure half-lives used for rate calculations for each treatment class are as follows:

- Corticosteroids: 7 days
- Immunosuppressants: 28 days
- Biologic agents (including Cimzia): 70 days

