8.1.3 Time-to-event analysis

Time-to-event analyses will be conducted for each Adverse Event of Interest.

Please refer to Section 3.6 for the assignment of treatment groups and to Section 3.2.1 for details on exposure times.

Cimzia vs. Comparator (acute event rules)

Per patient and Adverse Event of Interest, exposure time until the first occurrence of the AE is considered. Prior to the AE, at any given time after treatment start, the patient can be exposed to either of: Cimzia, Comparator, Overlap, or Gap (one at a time but with switches between them). Thus, up to the first occurrence of the AE, 4 exposure times are recorded, one for each treatment. The first occurrence of the AE is counted as event for the actual treatment where it occurred (i.e. exactly one of Cimzia, Comparator, Overlap, or Gap), and exposure time is censored for the remaining 3 treatments. If no AE of interest occurred, time will be censored at the end of exposure for all treatments. The comparison of interest is Cimzia vs. Comparator.

Any Cimzia vs. Comparator (acute event rules)

Per patient and Adverse Event of Interest, exposure time until the first occurrence of the AE is considered. Prior to the AE, at any given time after treatment start, the patient can be exposed to either of: Any Cimzia (i.e. Cimzia monotherapy or Overlap), Comparator, or Gap (one at a time but with switches between them). Thus, up to the first occurrence of the AE, 3 exposure times are recorded, one for each treatment. The first occurrence of the AE is counted as event for the actual treatment where it occurred (i.e. exactly one of any Cimzia, Comparator, or Gap), and exposure time is censored for the remaining 2 treatments. If no AE of interest occurred, time will be censored at the end of exposure for all treatments. The comparison of interest is Any Cimzia vs. Comparator.

Cimzia vs. Comparator (malignancy rules)

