8.2.2 Adverse Events

Any event reported by the investigator or found in the drug safety database excerpt is considered an adverse event. Investigator and drug safety AEs have been reconciled by the study physician to avoid over reporting.

When an AE is considered serious in either source, it is treated as serious in the analysis and the related coding data is used.

Events reported in the patient survey are not considered confirmed AEs and are excluded from the analysis.

AE tabulations will be done using malignancy rules (for malignancies) separately using acute event rules (all AEs) unless otherwise specified.

A summary of study-emergent AEs, including the number of events reported, the number and percentage of patients reporting at least one AE, the number and percentage of patients reporting at least one AE of Interest, the number and percentage of patients with at least one serious AE (SAE), and the number and percentage of deaths will be presented. In addition, the number and percentage of patients reporting at least one study-emergent treatment-related AE, the number and percentage of patients reporting at least one study-emergent treatment-related AE of Interest, and the number and percentage of patients with at least one study-emergent treatment-related SAE will also be reported. AE summaries will be produced on the enrolled cohort as well as the malignancy/acute event rules.

Study-emergent AEs are those which first occur or increase in relationship to treatment after the first dose of any CD drug following enrollment.

A breakdown of the number and percentage of patients reporting each AE as well as the number of AEs, categorized by SOC, HLT, and PT coded according to MedDRA, will be presented. Note that patients are only counted once within each SOC, HLT, or PT. Uncoded AEs will be summarized in unknown SOC, HLT and PT. This will be produced for the enrolled cohort as well as both the malignancy and acute event rules.

A further tabulation of these data, broken down by relationship to treatment, will be presented. Patients with multiple events within a particular body system or preferred term will be counted under the category of their most drug-related event within that SOC, HLT or PT. Relationship to treatment is categorized as related or not related as collected on the eCRF.

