11 APPENDICES

11.1 Appendix 1 – Treatment Allocation of Malignancies and Acute Adverse Events

Assumptions:

- Treatment periods described in the dosing column have the drug half-life added to the end of each treatment.
- Overlap is when comparator and Cimzia treatment periods overlap. The overlap can occur during the extended treatment for the drug half-life.
- Abbreviations; IC=Informed Consent Date, EoS= End of Study Date
- Gap and Overlap are not possible treatment groups for Malignancy Time at Risk as per SAP section 3.2.1.1 “Person-time at risk calculations for malignancy”. Overlap would be considered Cimzia and Gap would be assigned to the prior treatment.
- The dosing prior to IC only has an impact on malignancy time at risk. If a subject has no Cimzia dosing prior to IC it is considered to have had Comparator dosing prior to IC regardless of what is recorded in the dosing information.

#	Dosing prior to IC	Dosing during study (IC onwards)	Adverse Event	Treatment AE assigned to	Malignancy Time at Risk		Other AE Time at Risk			
					Cimzia	Comparator	Cimzia	Comparator	Gap	Overlap
1a	No Cimzia	Comparator > Cimzia > Comparator	None	N/A	Start of Cimzia to EoS	IC to Start of Cimzia	Start of Cimzia to Start of Second Period of Comparator	(IC to Start of Cimzia) plus (Start of Second Period of Comparator to EoS)	None	None
1b	Cimzia	Comparator > Cimzia > Comparator	None	N/A	IC to EoS	None	Start of Cimzia to Start of Second Period of Comparator	(IC to Start of Cimzia) plus (Start of Second Period of Comparator to EoS)	None	None

#	Dosing prior to IC	Dosing during study (IC onwards)	Adverse Event	Treatment AE assigned to	Malignancy Time at Risk		Other AE Time at Risk			
					Cimzia	Comparator	Cimzia	Comparator	Gap	Overlap
2a	No Cimzia	Comparator > Cimzia > Comparator	Malignancy during second period of Comparator	Cimzia	Start of Cimzia to Malignancy Start Date	IC to Start of Cimzia	Start of Cimzia to Start of Second Period of Comparator	(IC to Start of Cimzia) plus (Start of Second Period of Comparator to EoS)	None	None
2b	Cimzia	Comparator > Cimzia > Comparator	Malignancy during second period of Comparator	Cimzia	IC to Malignancy Start Date	None	Start of Cimzia to Start of Second Period of Comparator	(IC to Start of Cimzia) plus (Start of Second Period of Comparator to EoS)	None	None

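### Hypersensitivity cases are defined by a dose given that day or the day before, but 7/28/70-day windows assign them to a group, so in Overlap time a reaction to another biologic can count as Any Cimzia

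*SAP*

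**What the plan says.** **Case definition.** SAP 8.2.3: "Hypersensitivity reactions will be summarized as any TEAEs occurring on the same day or the day after injection was received", limited to a list of preferred terms. No drug is named. For anaphylaxis the same bullet gives no link to a dose date: "Anaphylactic reactions will be defined using an algorithmic approach as described in the" program guidance document. Protocol 5.2.5 is narrower in time and refers to an "acute hypersensitivity reaction occurring within 2 hours of drug administration".

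**Attribution.** Table 8.1 lists "Hyper/Anaphylactic reaction" as an acute event. SAP 8.2.2 says AE tabulations are done "separately using acute event rules (all AEs) unless otherwise specified", and no exception is written for hypersensitivity. SAP 3.2.1.3 sets the numerator "based on the date of the last dose received before event onset and treatment class-specific half-life exposure of the medication", with windows of 7 days for corticosteroids, 28 for immunosuppressants and 70 for biologics including Cimzia.

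**Groups.** SAP 3.6 divides acute events and person-time into Cimzia, Comparator, Overlap and Gap, and adds Any Cimzia as the sum of Cimzia and Overlap. Appendix 1 says of Overlap: "The overlap can occur during the extended treatment for the drug half-life". Its examples 6a and 6b assign a non-malignancy AE arising in Overlap to Overlap. SAP 8.1.3 repeats the pooling in its second contrast, where the states are "Any Cimzia (i.e. Cimzia monotherapy or Overlap), Comparator, or Gap".

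**The concern.** A hypersensitivity case exists only because a dose was given that day or the day before, so deriving it already requires a particular dose to be identified. The attribution rule does not use that dose. It asks which drugs are still inside a residual-exposure window, which is a different question for an immediate reaction. Where two drugs are inside their windows, the drug whose dose made the event qualify no longer decides the group.

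Switching is expected: SAP 3.6 says so, and SAP 8.1.1 plans a category for a TNF antagonist combined with an immunosuppressant. Overlap time will therefore not be empty. Protocol 6.1.1 lists hypersensitivity among the safety events to be investigated in addition to malignancy, and Protocol 6.2 links short-latency events to the start of a new treatment. A reader of the Any Cimzia row would take it as reactions to Cimzia, when part of it may be reactions to the next drug.

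**Working it through.** The plan states no rate, event count or power for hypersensitivity, so there is no figure to reproduce. The check applies the written rule to dated cases and then works out the effect on the ratio.

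**Step 1. Rule.** A drug counts as present from first dose to last dose plus its window (7, 28 or 70 days; SAP 3.2.1.3, Appendix 1). Cimzia and a comparator both present gives Overlap; neither gives Gap.

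**Step 2. Dated cases.**

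| Case | Group |
|---|---|
| Last Cimzia day 0; first dose of another biologic on day 14, 28, 56, 69 or 70; reaction same day | Overlap, so Any Cimzia |
| As above, first dose on day 70, reaction on day 71 | Comparator |
| As above, first dose on day 71 or 90 | Comparator |
| Reaction on a Cimzia injection day; corticosteroid last taken 7 / 8 days before | Overlap / Cimzia |
| Same; immunosuppressant 28 / 29 days before | Overlap / Cimzia |
| Same; other biologic 70 / 71 days before | Overlap / Cimzia |
| Only one drug inside its window | That drug's group |

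The first row is the misattribution. The last row shows that it is confined to Overlap.

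**Step 3. The two readings of injection.** If any product qualifies, the first row applies as shown. If only Cimzia qualifies, every case has a Cimzia dose within a day and so falls in Cimzia or Overlap. Comparator then has almost no qualifying events by construction, and a reaction to another drug enters Any Cimzia only if it falls within a day of a Cimzia dose.

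**Step 4. Effect on Any Cimzia vs Comparator (any-product reading).** Let T be Any Cimzia person-time, f its Overlap share, and λ the reaction rate to comparator drugs, assumed equal inside and outside Overlap. Let R be the true ratio: reactions to Cimzia per unit of Any Cimzia time, divided by λ.

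- Any Cimzia rate = (RλT + λfT) / T = λ(R + f)
- Comparator rate = λ
- Observed ratio = R + f
- Share of Any Cimzia events due to the other drug = f / (R + f)

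Neither R nor f is in the documents. Over an assumed range:

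| R | f = 0.1 | f = 0.3 | f = 0.5 |
|---|---|---|---|
| 0.5 | 0.6 (16.7%) | 0.8 (37.5%) | 1.0 (50.0%) |
| 1 | 1.1 (9.1%) | 1.3 (23.1%) | 1.5 (33.3%) |
| 2 | 2.1 (4.8%) | 2.3 (13.0%) | 2.5 (20.0%) |

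Entries are the observed ratio, with the other drug's share of events in brackets. Assigning by product dosed returns each ratio to R.

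**Step 5. Effect on Cimzia vs Comparator.** If the rate of reactions to Cimzia is also the same inside and outside Overlap, the Cimzia group keeps Rλ(1 − f)T events over (1 − f)T person-time, which is Rλ. The ratio stays at R. A share f of Cimzia reactions is lost to this contrast, but they remain in Any Cimzia.

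**The case against.** **The numerator rule can be read differently.** The last dose before onset in SAP 3.2.1.3 could mean the single most recent dose, which would give the reaction to the drug just administered. The Overlap group in 3.6, its use in 8.1.3 and examples 6a and 6b do not allow that reading. At best the sections conflict.

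**Injection may mean Cimzia only.** The definition comes from a Cimzia program document. The listed term for infusion site hypersensitivity points towards other products too. The text is unclear, and the narrow reading leaves nothing to compare.

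**The endpoint is minor and descriptive.** This largely stands. Malignancy is the primary outcome, all analyses are descriptive, and the SAP places hypersensitivity outside its official AEs of interest. Since 8.1.3 covers AEs of interest, its hazard ratios may not be run here. The acute-rule tabulations still are.

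**A reader might infer more than the documents support:**

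- That anaphylaxis has the same defect. The SAP gives it no dose-date link, the guidance document is not available, and it is unclear whether the protocol's 2-hour phrase covers it.
- That Cimzia vs Comparator is biased because Cimzia reactions move to Overlap. Their person-time moves too; under constant rates, events are lost without bias.
- That reactions cluster at first doses after a switch. The documents do not say so.
- That the Cimzia count is inflated by a stated percentage. Any such figure only restates an assumed switching rate and ignores the Overlap time added to the denominator.

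**Conclusion.** The concern holds for hypersensitivity in Overlap time. On the any-product reading, the written rules count reactions to another biologic, given within 70 days of the last Cimzia dose, in Any Cimzia. This overstates the number of Cimzia reactions and understates the number of Comparator reactions. On the Cimzia-only reading, the comparison is uninformative. Either way, the SAP must say whose dose qualifies and which group receives the event.

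The size cannot be fixed from the documents. The shift of f in the Any Cimzia ratio rests on a comparator reaction rate, and a mix of comparator products, that are the same inside and outside Overlap. If rates vary with time since starting a drug, the distortion could be larger or smaller. Confidence is high on the mechanism; there is no basis for a point estimate of its effect.

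**What to change.** In SAP 8.2.3 and Table 8.1:

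1. State that a qualifying injection or infusion may be of any CD biologic.
2. Assign each hypersensitivity event to the injected or infused product given that day or the day before. Use a both category only if Cimzia and another such product were given in that interval. Limiting this to injected or infused products matters: an oral comparator taken daily would otherwise turn the both category back into Overlap.
3. Use as denominator all person-time on that product, with or without other drugs.
4. Keep the five-group acute table as a sensitivity display, with Overlap cases shown by product dosed.
5. State whether the same rule applies to anaphylaxis, and reconcile the same-day or next-day definition with the 2-hour wording in Protocol 5.2.5.

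The cost is SAP wording and one extra derivation. The any-product definition already needs dose dates, but day-level dates may not be complete for every product: SAP 4.2 imputes partial medication dates, for example to the first or last day of a month or to the consent date. Cases that depend on a partial or imputed dose date should be flagged.
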